## 8.0 DATA MANAGEMENT

We will create a shared database with common data definitions. This database will be programmed in REDCap (Research Electronic Data Capture). REDCap is a secure, web-based application with the capacity for direct export to Excel and common statistical packages (SPSS, SAS, Strata, R). REDCap has electronic CRFs, real-time data entry validation, audit trails, user authentication, data logging and encryption. It is HIPAA compliant with mechanisms in place to ensure confidentiality.

Specific forms will be used for each component of the subject's progress. The forms and data dictionary will be available online for all individuals who perform data entry. Research personnel, trained on data definitions, will enter data via web-based data forms after abstraction from the primary medical record and source documents. The multisite feature of REDCap will be used to restrict data viewing by investigators. REDCap allows double-data entry on some or all of the data elements. We will apply this feature to predefined "key" variables. In addition, logical data checks will be used to assess data quality for mis-entry. Suspect data entries will be flagged for re-review and confirmation by the investigative team at each site. When data are complete and all suspect entries addressed for a time period, the database will be "locked" for analysis. Analysis will use only this final locked version.

## 9.0 SUBJECT PRIVACY / PROTECTED HEALTH INFORMATION

Protected health information (PHI) collected on the case report forms and via the electronic medical records will be stored in an encrypted research database. Only designated research staff will have access to the research database unless otherwise requested to the IRB by the Principal Investigator.

## **10.0 RISK/BENEFIT ASSESSMENT**

### **10.1 Potential Study Risks**

The primary risk is the loss of privacy and breach of confidentiality. There will be ongoing assessment of the security of the data systems to ensure that subject's PHI is protected.

### **10.2 Potential Benefits**

The potential benefit to study subjects is having their antiplatelet medication selected based on genotype. This may result in improved clinical outcomes. The potential benefits to the health system include: improved clinical outcomes for subjects and decreased cost in care. Our ultimate goal is to translate our molecular work into clinical practice. In particular, we believe that genotype in part predicts clinical outcome, and that identification of the genetic factors will assist in clinical management in the future.

### **10.3 Alternatives to Participation**

The patient has the option to not participate and not sign the informed consent. If a patient declines to participate, there is no effect on the patient's regular, ongoing clinical care.

### **10.4 Data and Safety Monitoring**

The Principal Investigator and Co-Investigators will be ultimately responsible for assuring the security of all computer systems to minimize risk to participants. Safety data such as major bleeding events and major cardiovascular events will be assessed six months after enrollment begins.

## Appendix A. Treatment recommendations handout for interventional cardiologist

Table 1. Treatment recommendations for antiplatelet therapy based on CYP2C19 genotype

Genotype	Phenotype	Description	Treatment a
CYP2C19 *1/*1	Extensive metabolizer (normal)	Two inferred normal alleles	Clopidogrel (Plavix) 75 mg per day
CYP2C19 *1/*17		One inferred normal allele One increased function allele	
CYP2C19 *17/*17		Two gain of function alleles	
CYP2C19 *1/*2	Intermediate metabolizer	One inferred normal allele One loss of function allele	Prasugrel (Effient) 10 mg per day b  Or  Ticagrelor (Brilinta) 90 mg twice daily c
CYP2C19 *1/*3		One inferred normal allele One loss of function allele	
CYP2C19 *2/*17		One loss of function allele One gain of function allele	
CYP2C19 *3/*17		One loss of function allele One gain of function allele	
CYP2C19 *2/*2	Poor metabolizer	Two loss of function alleles	Prasugrel (Effient) 10 mg per day b  Or  Ticagrelor (Brilinta) 90 mg twice daily c
CYP2C19 *3/*3		Two loss of function alleles	
CYP2C19 *2/*3		Two loss of function alleles	

Table 2. Switching recommendations based on CYP2C19 genotype

Genotype CYP2C19	Initial loading dose	Reload	Maintenance a
*1/*2, *1/*3, *2/*2, *3/*3, *2/*17, *3/*17	Clopidogrel 600 mg	Prasugrel 60 mg	Prasugrel 10 mg b
		Ticagrelor 180 mg	Ticagrelor 90 mg c
*1/*1, *1/*17, *17/*17	Prasugrel 60 mg	Not needed	Clopidogrel 75 mg
	Ticagrelor 180mg	Clopidogrel 300 mg	Clopidogrel 75mg

a Please consider all clinical contraindications before prescribing alternative antiplatelet agent. Prasugrel and ticagrelor are recommended only when not clinically contraindicated. See table 3 below

Table 3. Clinical Contraindications to Prasugrel or Ticagrelor

Prasugrel b	Ticagrelor c

 
Do not use prasugrel in patients with active bleeding or a history of transient ischemic attack or stroke.
 
Individual risks/benefits of prasugrel must be carefully considered in patients over age 75.
 
Do not start prasugrel in patients likely to undergo urgent coronary bypass graft surgery (CABG).
 
Consider prasugrel 5 mg per day for patients <60 kg.
 
	
 
Do not use ticagrelor in patients with active bleeding or a history of transient ischemic attack or stroke.
 
Do not start ticagrelor in patients likely to undergo urgent coronary bypass graft surgery (CABG).
 
Do not use maintenance aspirin dose above 100 mg in combination with ticagrelor.
 
Avoid with strong CYP3A inhibitors or inducers.
 

1. Scott, S.A. et al. Clinical Pharmacogenetics Implementation Consortium Guidelines for CYP2C19 Genotype and Clopidogrel Therapy: 2013 Update. *Clin Pharmacol Ther* **94**, 317-23 (2013).

## Appendix B

### Participant Survey- Pharmacogenetic testing

#### Demographics

1. Name: \_\_\_\_\_

2. Age: \_\_\_\_\_

3. Sex:

- Male
- Female

4. Race (check all that apply):

- White
- Black/African-American
- Asian
- American Indian/ Alaska Native
- Native Hawaiian/ Pacific Islander
- Other

5. Ethnicity:

- Hispanic
- Non-Hispanic

6. Educational level:

- Less than high school
- High school graduate (or GED)
- Some college/ university
- College/university graduate
- Post college/ university degree
- Not provided

7. What is your current occupational status? (circle)

- Employed
- Unemployed
- Homemaker
- Student
- Retired
- Disabled
- Other, please specific \_\_\_\_\_

8. What is your marital status? (circle)

- Married
- Living as married
- Divorced
- Widowed
- Separated
- Single, never been married

9. What is your combined annual income (total pre-tax income from all sources earned in the past year)?

- \$0-\$9,999
- \$10,000-\$14,999
- \$15,000-\$19,999
- \$20,000-\$34,999
- \$35,000-\$49,999
- \$50,000-\$74,999
- \$75,000-\$99,999
- \$100,000-\$199,999
- \$200,000 or more
- Choose not to respond

10. How would you rate your current health

- Excellent
- Good
- Fair
- Poor

11. Have you ever experienced side effects due to your medications?

- No
- Yes, mild

Yes, severe

12. How confident are you in filling out forms in a doctor's office by yourself?

- Extremely
- Quite a bit
- Somewhat
- A little bit
- Not at all

**The following section includes questions about the role of genetics in health and disease. When we refer to a variant, we are referring to a change in a gene which may or may not be harmful.**

Please circle one number to indicate how much you agree or disagree with each statement.

	Strongly Agree	Agree	Neither agree nor disagree	Disagree	Strongly disagree
13. A health care provider can always tell a person their exact chance of developing a disease based on the results from genetic testing.	1	2	3	4	5
14. Even if a person has a variant in a gene that affects their risk of a disease, they may not develop that disease.	1	2	3	4	5
15. Genetic testing may find variants in a person's genes that may determine how they respond to certain medicines.	1	2	3	4	5
16. A person's health habit, like diet and exercise, can affect whether or not their genes can cause disease.	1	2	3	4	5
17. Genetic variants in a gene can change over a person's lifetime.	1	2	3	4	5

18. On a scale of 1 to 5 (1 being "Not at all important" and 5 being "very important"), how important is it to you to learn more about how your genes affect your chance of experiencing a side effect from a medication?

Not At All Important      1      2      3      4      5      Very Important

19. **On a scale of 1 to 5 (1 being "Not at all important" and 5 being "very important"), how important is it to you to learn more about how your genes may help in predicting which medications will work for you?**

[figure not shown]
20. Before participating in this study how aware were you about the use of genetic testing to predict whether certain medications will work for you?

- Aware
- Not aware

21. Did you receive genetic test result regarding CYP2C19 genotyping?

- Yes
- No
- Unsure

22. If yes in 21. **On a scale of 1 to 5 (1 being "not at all clear" and 5 being "very clear"), how clearly did you understand the PGx test results as it related to your antiplatelet medication?**

23. If applicable, what did you find unclear about your CYP2C19 test result?

---

---

Reminder, a pharmacogenetic test is a type of genetic test that could allow doctors to choose the right drug that will work for a patient while avoiding using certain drugs that may cause side effects.

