**To what extent do you agree or disagree with the following statements?**

	Strongly agree	Agree	Neither agree nor disagree	Disagree	Strongly disagree
24. I feel comfortable about the pharmacogenetic tests that might be offered to me, if they could predict if a medication would work for my condition.	1	2	3	4	5
25. I feel comfortable about the pharmacogenetic tests that might be offered to me, if they could predict the correct dose of the medication that I needed.	1	2	3	4	5
26. I feel comfortable about the pharmacogenetic tests that might be offered to me, if they could predict a mild side effect.	1	2	3	4	5
27. I feel comfortable about the pharmacogenetic tests that might be offered to me, if they could predict a serious side effect.	1	2	3	4	5
28. I feel comfortable about the pharmacogenetic tests that might be offered to me, if they could explain a family history of medication side effect or nonresponse.	1	2	3	4	5
29. It is important that my health care provider tells me about these pharmacogenetic tests, before any of them are done.	1	2	3	4	5
30. If these pharmacogenetic tests were part of my usual blood work it is important that my health care provider seek separate approval from me, specifically for the pharmacogenetic tests.	1	2	3	4	5

31. If I had to pay for the pharmacogenetic tests myself, financial costs would be one of my concerns about taking these tests.	1	2	3	4	5
32. If I took the test, I would be concerned that insurance companies may use the pharmacogenetic test results to deny healthcare coverage.	1	2	3	4	5
33. If I took the test, I would be concerned about the effect of the pharmacogenetic test results on my employment opportunities.	1	2	3	4	5

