## Appendix C

### Provider Survey- Pharmacogenetic testing

#### Demographics

1. Sex:

- Male
- Female

2. Race (check all that apply):

- White
- Black/African-American
- Asian
- American Indian/ Alaska Native
- Native Hawaiian/ Pacific Islander
- Other

3. Ethnicity:

- Hispanic
- Non-Hispanic

4. Year of graduation from medical school: \_\_\_\_\_

5. Medical Specialty:

- Internal medicine / family medicine/ general practice
- Cardiology
- Gastroenterology
- Genetics
- Oncology
- Surgery
- Other: \_\_\_\_\_

6. Where do you primarily practice?

- HUP
- PPMC
- PAH
- VA hospital
- Other: \_\_\_\_\_

Pharmacogenetic (PGx) testing: Testing to predict likelihood of drug toxicity or therapeutic efficacy. Testing identifies genetic variants in genes that may affect drug disposition (e.g., metabolism) or drug target resulting in increased risk for an adverse drug reaction or low likelihood of responding to a drug, respectively.

7. I feel well-informed about the role of PGx testing in therapeutic decision-making.

- Strongly agree
- Somewhat agree
- Neutral
- Somewhat disagree
- Strongly disagree
- Prefer not to answer

8. I believe that PGx testing is or will soon become a valuable tool to predict risk of adverse events or likelihood of effectiveness.

- Strongly agree
- Somewhat agree
- Neutral
- Somewhat disagree
- Strongly disagree
- Prefer not to answer

9. Had you heard of pharmacogenetic (PGx) testing before this survey?

- Yes
- No

10. Are you aware that the Food and Drug Administration (FDA) has revised drug labels to include information about pharmacogenetics?

- Yes
- No

11. Please indicate where and/or how you have learned about pharmacogenetics. (*Please check all that apply.*)

- Genetics training in medical school
- Genetics training in residency
- Continuing medical education (CME) meeting, in-person course, grand rounds
- CME distance learning (mail or web-based)
- Journals
- Colleagues
- Other (*Please specify.*) \_\_\_\_\_
- I have not had any education about pharmacogenetics.

12. In your opinion, what is the **BEST** way to educate physicians about PGx testing? (*Please select only one response.*)

- Genetics training in medical school
- Genetics training in residency
- Continuing medical education (CME) meeting, in-person course, or grand rounds
- CME distance learning (mail or web-based)
- Journals
- Grand rounds or other types of in-house seminars
- Other (*Please specify.*) \_\_\_\_\_
- Genetics education is not necessary

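### The patient survey puts a benefits-only description of the test directly before its attitude items, and the paper form carries the participant's name with no coding described

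*Protocol*

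**What the plan says.** Patient and prescriber attitudes are a stated objective (Protocol synopsis and section 3.0) and a tertiary endpoint (section 4.3). Section 7.3 plans to tabulate them, with no test and no sample size. Section 6.5 describes one paper survey for patients at 3 months, without distinguishing the arms.

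Appendix B contains that survey. After item 23, and directly before items 24-33, a reminder states that "a pharmacogenetic test is a type of genetic test that could allow doctors to choose the right drug that will work for a patient". The second half of its sentence names one more advantage, namely fewer side effects through avoiding certain medicines. The items that follow fall into three kinds:

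- comfort with testing under a stated condition, for example "I feel comfortable about the pharmacogenetic tests that might be offered to me, if they could predict if a medication would work for my condition";
- prior notice and approval, for example "It is important that my health care provider tells me about these pharmacogenetic tests, before any of them are done";
- concerns about cost, insurance and employment, for example "If I took the test, I would be concerned that insurance companies may use the pharmacogenetic test results to deny healthcare coverage".

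The provider survey in Appendix C describes the same kind of test as "Testing to predict likelihood of drug toxicity or therapeutic efficacy".

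Item 1 of the patient form is the participant's name. Occupational status (with disability as one option), income, self-rated health and receipt of a CYP2C19 result are asked on the same form. The provider form has no name line. Section 10.1 states: "The primary risk is the loss of privacy and breach of confidentiality". Section 9.0 provides an encrypted database with restricted access for identifiable data from case report forms and electronic records. Neither section mentions the paper survey or a study code for it.

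**The concern.** A survey that measures attitudes should describe its subject neutrally just before asking about it. Here the respondent reads two advantages and no limitation, then rates comfort with testing. If the description moves answers, the movement becomes part of the reported percentage. Because a single form is described for all patients, no group without the preamble exists against which to detect or remove it.

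The name line is a separate matter. It puts a direct identifier on a paper document that also holds socio-economic and health answers and views on misuse of genetic results, in a study that ranks loss of privacy first among its risks.

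At stake are the credibility of one descriptive endpoint and an avoidable exposure of identifiable data. The treatment comparison is not affected.

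**Working it through.** The plan gives no figure on this point, so the check is a comparison of texts, followed by a note on scale.

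**1. Content of the reminder.** It names two benefits: a drug that works, and avoidance of drugs with side effects. It names no limits, errors or drawbacks. The only hedge is the modal verb that presents the benefits as possible.

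**2. Content of the provider definition.** Appendix C speaks of predicting a likelihood, of toxicity or of efficacy. It too lists no limitations, but it is probabilistic and does not speak of a right drug that will work. More neutral wording therefore already exists in the same protocol.

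**3. What follows the reminder.** Of the ten items 24-33:

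| Items | Subject | Count |
|---|---|---|
| 24-28 | Comfort, if the test predicts or explains something useful | 5 |
| 29-30 | Prior notice and separate approval | 2 |
| 31-33 | Cost, insurance and employment concerns | 3 |

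5 + 2 + 3 = 10. The reminder and items 24-28 point the same way, so a shift towards comfort is most plausible there. In items 31-33 agreement is the unfavourable answer, and nothing in the documents shows how the reminder or the name line acts on them. The importance questions, items 18-19, come before the reminder and cannot be framed by it.

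**4. Scale, under assumptions.** The 95% half-width of a tabulated proportion is 1.96 × √(p(1 − p)/n). Take p = 0.5. Section 7.5 plans about 250 per group, hence 2 × 250 = 500 forms at full return. No return rate is given, so half return (250 forms) is shown as well.

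- n = 500: 1.96 × √(0.25/500) = 0.044, or 4.4 points.
- n = 250: 1.96 × √(0.25/250) = 0.062, or 6.2 points.

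Suppose, purely as an assumption, that the wording shifts agreement by 5 to 10 points. With 500 forms the whole range exceeds the sampling error. With 250 forms only shifts above 6.2 points do. This shows when a shift would matter. It does not estimate the shift.

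**5. The identifier.** Answers must be linked to the arm and the genotype record, so some identifier is needed. A study ID serves that purpose. Sections 8.0 and 9.0 describe electronic entry, encryption and access control. They leave open how the named paper sheet is handled before and after entry.

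**The case against.** The strongest reply is that the form is not one-sided and the reminder may do little. Items 24-28 each state their own condition, so respondents know they are judging a hypothetical useful test. Items 13-14 probe overclaims about genetic testing, item 23 asks what was unclear, and items 31-33 raise concerns in the same block as the reminder. All of this is correct. It limits how large an effect one should expect, but it does not make the preamble neutral. It also means that rewording the reminder leaves the conditions inside items 24-28 in place.

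A reader might go further and infer that the reported attitudes are in fact biased in favour of testing, or that a named form suppresses fears about insurers and employers. The documents support neither. The size of any framing effect is unknown, and writing one's name above such questions could as well raise stated concern as lower it. Nor do the differing descriptions in the two surveys damage a planned analysis: no comparison of patients with prescribers is planned. No difference in wording between the arms is described either.

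On privacy, the protections in section 9.0 stand once data are in the database, and the need for linkage is real. What remains is narrow: the link does not require a name, and the handling of the paper form is not described.

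Finally, the SAP is written in the past tense, with analyses after May 31, 2017, and its objectives and outcome definitions omit patient attitudes. Forms may already have been collected. That changes the remedy, not the observation.

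**Conclusion.** The point holds as a cheap improvement. The reminder before items 24-33 gives only benefits and may move tabulated attitudes by an unknown amount, most plausibly towards comfort on items 24-28. An effect on items 31-33 is not shown. Separately, a direct identifier stands on a sensitive paper form without any described coding, in a study that names privacy loss as its primary risk. This second part needs no assumption about bias.

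The consequence is small: the endpoint is tertiary and descriptive, and the primary endpoint and its sample size are untouched. The half-widths of 4.4 and 6.2 points rest on 50% agreement and on assumed returns of 500 and 250 forms. The shift of 5 to 10 points is an assumption without support in the documents.

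**What to change.** - Replace the reminder with a neutral lay version of the Appendix C definition. It could say that the test looks at genes that may affect how a medicine works or causes side effects, and that the result may or may not change the choice of medicine.
- Replace the name line with the study ID. This keeps the link to arm and genotype. It does not make the form anonymous, and the form should not be presented as such.
- Where forms have already been collected, record the form version, report the exact wording with the results as a limitation, and separate names from stored answers.

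The cost is two lines on the form and a minor amendment. The one downside is that form versions must be tracked if both are in use.

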**To what extent do you agree or disagree with the following statements?**

	Strongly agree	Agree	Neither agree nor disagree	Disagree	Strongly disagree
24. I feel comfortable about the pharmacogenetic tests that might be offered to me, if they could predict if a medication would work for my condition.	1	2	3	4	5
25. I feel comfortable about the pharmacogenetic tests that might be offered to me, if they could predict the correct dose of the medication that I needed.	1	2	3	4	5
26. I feel comfortable about the pharmacogenetic tests that might be offered to me, if they could predict a mild side effect.	1	2	3	4	5
27. I feel comfortable about the pharmacogenetic tests that might be offered to me, if they could predict a serious side effect.	1	2	3	4	5
28. I feel comfortable about the pharmacogenetic tests that might be offered to me, if they could explain a family history of medication side effect or nonresponse.	1	2	3	4	5
29. It is important that my health care provider tells me about these pharmacogenetic tests, before any of them are done.	1	2	3	4	5
30. If these pharmacogenetic tests were part of my usual blood work it is important that my health care provider seek separate approval from me, specifically for the pharmacogenetic tests.	1	2	3	4	5

31. If I had to pay for the pharmacogenetic tests myself, financial costs would be one of my concerns about taking these tests.	1	2	3	4	5
32. If I took the test, I would be concerned that insurance companies may use the pharmacogenetic test results to deny healthcare coverage.	1	2	3	4	5
33. If I took the test, I would be concerned about the effect of the pharmacogenetic test results on my employment opportunities.	1	2	3	4	5

## Appendix C

### Provider Survey- Pharmacogenetic testing

#### Demographics

1. Sex:

- Male
- Female

2. Race (check all that apply):

- White
- Black/African-American
- Asian
- American Indian/ Alaska Native
- Native Hawaiian/ Pacific Islander
- Other

3. Ethnicity:

- Hispanic
- Non-Hispanic

4. Year of graduation from medical school: \_\_\_\_\_

5. Medical Specialty:

- Internal medicine / family medicine/ general practice
- Cardiology
- Gastroenterology
- Genetics
- Oncology
- Surgery
- Other: \_\_\_\_\_

6. Where do you primarily practice?

- HUP
- PPMC
- PAH
- VA hospital
- Other: \_\_\_\_\_

Pharmacogenetic (PGx) testing: Testing to predict likelihood of drug toxicity or therapeutic efficacy. Testing identifies genetic variants in genes that may affect drug disposition (e.g., metabolism) or drug target resulting in increased risk for an adverse drug reaction or low likelihood of responding to a drug, respectively.

7. I feel well-informed about the role of PGx testing in therapeutic decision-making.

- Strongly agree
- Somewhat agree
- Neutral
- Somewhat disagree
- Strongly disagree
- Prefer not to answer

8. I believe that PGx testing is or will soon become a valuable tool to predict risk of adverse events or likelihood of effectiveness.

- Strongly agree
- Somewhat agree
- Neutral
- Somewhat disagree
- Strongly disagree
- Prefer not to answer

9. Had you heard of pharmacogenetic (PGx) testing before this survey?

- Yes
- No

10. Are you aware that the Food and Drug Administration (FDA) has revised drug labels to include information about pharmacogenetics?

- Yes
- No

11. Please indicate where and/or how you have learned about pharmacogenetics. (*Please check all that apply.*)

- Genetics training in medical school
- Genetics training in residency
- Continuing medical education (CME) meeting, in-person course, grand rounds
- CME distance learning (mail or web-based)
- Journals
- Colleagues
- Other (*Please specify.*) \_\_\_\_\_
- I have not had any education about pharmacogenetics.

12. In your opinion, what is the **BEST** way to educate physicians about PGx testing? (*Please select only one response.*)

- Genetics training in medical school
- Genetics training in residency
- Continuing medical education (CME) meeting, in-person course, or grand rounds
- CME distance learning (mail or web-based)
- Journals
- Grand rounds or other types of in-house seminars
- Other (*Please specify.*) \_\_\_\_\_
- Genetics education is not necessary

13. How often do you order PGx tests?

- Never
- 1-2 times per year
- 3-10 times per year
- 11-25 times per year
- More than 25 times per year
- Unsure

14. In general, how likely are you to order a PGx test that predicts the **efficacy** of a drug for an individual patient?

- Very likely
- Somewhat likely
- Neutral
- Somewhat unlikely

Very unlikely

15. In general, how likely are you to order a PGx test that predicts the **safety** of a drug for an individual patient?

Very likely

Somewhat likely

Neutral

Somewhat unlikely

Very unlikely

16. In your opinion, when deciding whether or not to order a pharmacogenetic test to **determine a potential adverse drug reaction** for an individual patient, how important are the following considerations?

	Very important	Somewhat important	Neutral	Somewhat unimportant	Not at all important
a. Severity of the potential drug reaction.					
b. Prevalence of the potential drug reaction.					
c. Predictive value of the test.					
d. Availability of other clinical testing to monitor drug toxicity.					
e. Severity of the condition being treated.					
f. Prevalence of genetic variant (positive test result).					
g. Inclusion of information about the test on the drug label/package insert.					
h. Availability of practice guidelines for test use and interpretation.					
i. Insurance reimbursement of test.					
j. Cost of the test.					
k. Turnaround time for the test results to be returned.					
l. Cost of the drug for which test is ordered.					
m. Availability of an alternative drug.					

17.

18. In your opinion, when determining the value of a PGx test to identify a patient who is **unlikely to respond to a drug (efficacy)**, how important are the following considerations

	Very important	Somewhat important	Neutral	Somewhat unimportant	Not at all important
a. Likelihood of non-response to the drug.					
b. Predictive value of the test.					
c. Availability of other clinical testing to monitor drug response.					
d. Urgency of treatment.					
e. Severity of the condition being treated.					
f. Likelihood of genetic variant (positive test result).					
g. Inclusion of information about the test on the drug label.					
h. Availability of practice guidelines for test use and interpretation.					
i. Insurance reimbursement of the test.					
j. Cost of the test.					
k. Turnaround time for the test results to be returned.					
l. Cost of the drug for which test is ordered..					
m. Availability of an alternative drug.					

19. Please indicate which professional or group should have **PRIMARY** responsibility to discuss PGx test result with the patient.

- Physician ordering the test
- Primary care provider
- Geneticist / Genetic Counselor

- Pharmacist
- Genetic testing lab
- Don't know

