#### 4.3 Tertiary Endpoints

- a. Additional implementation metrics
  - a. Number of genotype results returned
  - b. Average genotype test completion time
  - c. Genotype assay failure rate (inconclusive test result)
  - d. Number/reason for screening failure
  - e. Time from test order to result in medical record
- b. Patient attitudes towards PGx testing as determined by questionnaire will be completed at the 3 month phone follow-up.
- c. Prescriber attitudes towards PGx testing as determined by questionnaire that will be administered at the start and end of the study.

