### **6.6 Provider attitudes towards pharmacogenetic testing**

Treating physicians participating in the study will complete a survey at baseline and 1 year to assess their attitudes towards pharmacogenetic testing and needs for medical education in this area (Appendix C).

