### **7.3 Tertiary endpoints**

We will also tabulate the number of genotype results returned, the average genotype test completion time, the genotype assay failure rate, the number of and reason for screening failure, time from test order to result in medical record, and patient/prescriber attitudes towards PGx test results.

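### Provider survey item 12 names grand rounds in two of its single-choice answers, so those two rows cannot be interpreted separately

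*Protocol*

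**What the plan says.** Protocol section 6.6 plans two rounds of the provider survey: "Treating physicians participating in the study will complete a survey at baseline and 1 year". It gives the purpose as "to assess their attitudes towards pharmacogenetic testing and needs for medical education in this area". Section 4.3 lists the survey among the tertiary endpoints: "Prescriber attitudes towards PGx testing as determined by questionnaire that will be administered at the start and end of the study". Section 7.3 says that "patient/prescriber attitudes towards PGx test results" will be tabulated.

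The form is in Appendix C. Item 12 asks for the single best way to educate physicians, with the instruction "Please select only one response". Two of its eight options are "Continuing medical education (CME) meeting, in-person course, or grand rounds" and "Grand rounds or other types of in-house seminars". The item does not say how to choose between them.

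Item 11, just before it, asks where respondents have learned about pharmacogenetics. It names grand rounds once, in "Continuing medical education (CME) meeting, in-person course, grand rounds", and lets respondents tick every option that applies.

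Neither document has a rule for combining the two item 12 options. The SAP lists no provider-survey outcome.

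**The concern.** The options of a single-choice item should not overlap. Here a prescriber whose answer is grand rounds has two correct boxes and may use one. Each box also bundles grand rounds with something else: CME meetings and courses in one, in-house seminars in the other. The number who prefer grand rounds therefore cannot be read from either row.

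Item 12 is the only item shown in Appendix C that asks for the preferred teaching method, and section 6.6 makes education needs a purpose of the survey. A table of answers to a question about the best method will be read for which row is highest. That reading could be wrong if support for grand rounds is divided between two rows.

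**Working it through.** The plan states no figure to reproduce. The check is a comparison of the wording, followed by an illustration.

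**Comparison of items 11 and 12 (Appendix C)**

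| | Item 11 | Item 12 |
|---|---|---|
| Response format | all that apply | one only |
| Options naming grand rounds | 1 | 2 of 8 |
| Can grand-rounds answers split? | no | yes |

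**What the table for item 12 can show.** Let g be the share of respondents who prefer grand rounds, c the share who prefer a CME meeting or course, h the share who prefer other in-house seminars, and s the unobserved fraction of grand-rounds supporters who tick the CME option. Then:

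- CME row = c + s·g
- in-house row = h + (1 − s)·g
- sum of the two rows = c + h + g, which does not contain s

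The data do not give s, c or h separately. So g is known only to lie between 0 and the sum of the two rows. The other six rows contain no g and are unaffected.

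**Illustration.** These shares are assumptions, not figures from the documents: g = 35%, c = 10%, h = 0, best other method o = 30%. The remaining 25% is spread over the other options, and none of them matters here.

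| s | CME row: 10 + 35s | In-house row: 35(1 − s) | Other method | First | Sum of two rows |
|---|---|---|---|---|---|
| 0 | 10% | 35% | 30% | in-house | 45% |
| 0.25 | 18.75% | 26.25% | 30% | other | 45% |
| 0.50 | 27.5% | 17.5% | 30% | other | 45% |
| 0.75 | 36.25% | 8.75% | 30% | CME | 45% |
| 1 | 45% | 0% | 30% | CME | 45% |

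Opinion is the same in every line; only s changes.

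**When another method can come first.** It needs both c + s·g < o and h + (1 − s)·g < o. Some s meets both only if c + h + g < 2o, that is, if the sum of the two rows is less than twice the other method's share.

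- g = 35%, c = 10%, o = 30%: 45 < 60, so it can. The range is 1 − 30/35 = 0.14 < s < (30 − 10)/35 = 0.57.
- g = 40%, c = 10%, o = 30%: 50 < 60, so it can. The range is 1 − 30/40 = 0.25 < s < (30 − 10)/40 = 0.50, with ties at both ends.
- g = 50%, c = 10%, o = 25%: 60 > 50, so it cannot. First place moves only between the two overlapping rows.

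The split can thus change the leading row, but whether it can hand first place to an unrelated method depends on the shares.

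**The case against.** The strongest reply is that very little rests on this. Section 7.3 plans a tabulation, with no ranking, no test and no comparison of item 12 between rounds. The tertiary endpoint is attitudes towards testing, whereas item 12 asks about teaching methods, so the link to a named endpoint is loose. Respondents might also read one option as formal CME and the other as local teaching, in which case few answers would split. All of this limits the importance of the point. It does not remove the overlap, because nothing on the form enforces that reading and section 6.6 makes education needs a purpose of the survey.

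A reader might infer three stronger things that the documents do not support:

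- **That the whole item is unreadable.** Six of the eight rows can be compared with one another, and the sum of the two overlapping rows is sound.
- **That votes did split, or that the split differed between rounds.** The form shows only that they can.
- **That a popular grand-rounds option would necessarily lose first place to another method.** With 40% for grand rounds divided evenly, the CME row is 20% plus the true CME share. Against a rival at 25%, the CME row leads as soon as that share exceeds 5%.

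**Conclusion.** The point holds as a minor wording error in the instrument. As written, item 12 cannot give a count for grand rounds. The separate positions of the two overlapping rows, and possibly first place, should not be interpreted.

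That conclusion follows from the wording alone and needs no assumption. The percentages are illustrative, because the documents give neither the number of prescribers nor any expected distribution of answers. The effect is confined to one descriptive item; no primary or secondary endpoint and nothing in the SAP depends on it.

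**What to change.** For any round still to be run, name grand rounds in one option of item 12 only, and treat it the same way in item 11. There are two consistent ways:

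1. Keep grand rounds with CME meetings and courses in both items, and reword the second item 12 option to cover other in-house seminars only.
2. Take grand rounds out of the CME option in both items and give it its own place in each.

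Changing item 12 alone by the second route would leave grand rounds under CME in item 11 and under in-house teaching in item 12.

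For any round already collected on the current form, report the two overlapping rows as one category at both time points, and do not interpret them separately. This may be the only remedy left: the SAP is written in the past tense and places all analyses after May 31, 2017, although the documents do not say when the surveys were completed. If only the second round uses a corrected form, the combined category still covers the same methods in both rounds.

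The cost is a wording change to one or two survey items, or merging two rows of a table. The downside is that merged data cannot separate CME meetings from grand rounds or in-house seminars, but the current form does not separate them cleanly either.
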